1.1 Background

Multimodal analgesia has played a key role in decreasing postoperative pain in patients undergoing colorectal operations. Recently, its role in decreasing oral morphine equivalents (OME) has been shown to decrease length of stay (LOS) and decrease the risk of postoperative ileus (POI) at Mayo ¹. Multimodal analgesia and limiting systemic opiate use are critical components in enhanced recovery pathways. Numerous studies have assessed the best agent and mode of neuraxial blockade. Its role in decreasing narcotic use and improving POI and LOS has been well-studied ²⁻⁴. Currently at our institution, single injection intrathecal hydromorphone analgesia is routinely used in addition to systemic, non-opiate analgesia (e.g., gabapentin, acetaminophen, non-steroidal anti-inflammatory medications).

Transversus abdominis plane (TAP) block is an alternative to neuraxial analgesia, and it has had promising results for analgesia after colorectal surgery ⁴⁻⁶. A limitation of bupivacaine TAP blockade is the relatively short duration of effect, ranging on average from 6-12 hours ⁷. Liposomal bupivacaine (EXPAREL) is a relatively new product currently FDA-approved for wound infiltration with an analgesic effect for 72 hours. EXPAREL has been shown to be safe and effective.

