3.1 General Design

This study is prospective, randomized trial in which EXPAREL TAP block is compared to standard IT opioid administration, in relieving postoperative pain, decreasing length of stay, and use of narcotic medication. Subjects will be screened at outpatient clinic visit appointments and interested qualified subjects will be consented and offered participation in this trial. All enrolled patients will be entered by the surgeon through written informed consent. All data will be entered in a prospective automated institutional database.

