7.2 Sample size

The two primary endpoints of interest are pain scores over 48 hours post-surgery and the amount of narcotic medication used, standardized to OME, over 48 hours post-surgery. The pain score endpoint will be summarized as area under the curve (AUC), normalized for the total time of observation. A sample size of 100 patients per arm provides 80% power to detect an effect size of 0.40 using a two group t-test with a 0.05 two-sided significance level. The effect size is the expected difference in the mean AUCs divided by the within group standard deviation. A difference of 0.5 standard deviations in pain scores has been demonstrated to be clinically meaningful in the QOL literature. This study is adequately powered to detect this; a sample size of 100 patients in each group has 94% power to detect a difference in the mean AUC pain scores between the two groups of 0.50 standard deviations. The narcotic medication use (standardized OME) will be the cumulative use over the 48 hour period. It is also felt that a difference of 0.4 standard deviations in the mean narcotic use (standardized to OME) between the groups is clinically meaningful.

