7.3 Analysis plans

Patient Population(s) for Analysis

The patient for the primary analysis will be all randomized patients who did not withdraw prior to the initiation of anesthesia. The numbers of patients that withdraw prior to undergoing surgery will be monitored for imbalances between the arms.

Primary analysis plan

The primary analysis will be a modified intent-to-treat analysis. This means it will be an analysis of all randomized patients who did not withdraw prior to surgery according to the arm to which they were randomized.

The mean pain scores over 48 hours will be summarized as the area under the curve (AUC) of the observed pain score (y-axis) plotted by the time it was measured (x-axis). The difference in mean AUCs of the two groups will be evaluated using a two-sample t-test. In addition, the cumulative narcotic use over the 48 hour period will be determined for each patient (standardized OME). The difference in mean standardized OME will be compared with a two-sample test. If the data are skewed, a two-sample t-test will be performed on the logged values of OME or a Wilcoxon rank sum test will be used on the untransformed data. A two-sided p-value will be declared statistically significant for each primary endpoint. This will mean that the overall two-sided level of significance for the trial will be 0.10.

In addition to looking at the summary of the pain scores and OME scores, we will also plot these values over time and determine whether there are differences at individual time points.

Secondary analysis plan

The mean length of stay will be compared between the two groups with a two-sample test. If there are no outliers, a two-sample t-test will be used. If there are outliers, a Wilcoxon rank sum test will be used. A chi-square test (or Fisher's exact test) will be used to compare the rates of POI, need for a PCI and post-operative hypotension.

Comparisons will be made between the randomized groups of the baseline variables (patient, disease, and surgical) to determine if there were any randomization imbalances. If imbalances are found, a secondary analysis will be done using linear regression and adding the variables that were not balanced between the groups.

Descriptive Statistics

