Univariable descriptive statistics will be calculated for all variables; categorical variables will be summarized as counts (relative frequencies) and continuous variables will be summarized as mean \pm standard (SD) and median (min value, max value).

Handling of Missing Data

Missing data will prompt individual review of the patient's electronic record to obtain missing variables. Analyses will be done using all patients who have the necessary data for the analysis. If the amount of missing data within an analysis is greater than 10%, imputation methods will be used and the data re-analyzed as a sensitivity analysis.

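### Does the plan need a rule for the 48-hour opioid total when a patient goes home before hour 48?

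*Combined protocol and SAP*

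**What the plan says.** Two places define the endpoint. Section 7.2: "The narcotic medication use (standardized OME) will be the cumulative use over the 48 hour period". Section 7.3 (Primary analysis plan): "the cumulative narcotic use over the 48 hour period will be determined for each patient (standardized OME". Neither divides the total by time observed. The other co-primary endpoint is treated differently in Section 7.2: "The pain score endpoint will be summarized as area under the curve (AUC), normalized for the total time of observation".

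The primary analysis is modified intent-to-treat: "it will be an analysis of all randomized patients who did not withdraw prior to surgery". Under Handling of Missing Data, the electronic record is searched first. Then: "Analyses will be done using all patients who have the necessary data for the analysis". Then: "If the amount of missing data within an analysis is greater than 10%, imputation methods will be used", as a sensitivity analysis.

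On discharge, the Study Summary gives participation of 2 to 5 days, and Section 3.3 makes length of stay a secondary endpoint. Section 6 describes follow-up to about 30 days for safety only. Section 5.8 says that the trial is not blinded.

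**The concern.** A sum over a fixed window depends on how long the patient is watched. The window starts after surgery, so a patient who leaves on the second day can go home short of hour 48, and whatever opioid is taken at home goes unrecorded. The text then allows two readings. In one, the inpatient sum stands as the 48-hour total and the unseen hours enter as zero. In the other, the total is missing and the patient drops out of the OME comparison.

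The choice matters only if early discharge differs by arm, and the design makes that conceivable. Section 3.1 compares the arms "in relieving postoperative pain, decreasing length of stay, and use of narcotic medication", and staff know the allocation. A truncated sum would flatter the arm that leaves sooner. Dropping early leavers would work against that arm if they are the patients who need less opioid. Every patient has some inpatient sum, so neither the record search nor the 10% trigger need notice the problem. At stake is a false claim, or a diluted true one, on a co-primary endpoint.

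**Working it through.** **The plan's own figures first.** Inputs from Section 7.2: 100 per arm, two-sided 0.05, effects of 0.40 and 0.50 SD. Power is Φ(d√(n/2) − 1.96).

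- d = 0.40: Φ(0.40 × 7.071 − 1.96) = Φ(0.868) = 80.7% (80.4% with the t distribution); stated 80%.
- d = 0.50: Φ(0.50 × 7.071 − 1.96) = Φ(1.576) = 94.2% (94.0% with t); stated 94%.

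Both reproduce, and the concern does not touch them. The pain endpoint is already divided by observation time.

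**How early can discharge be?** Safety follow-up runs to 30 days, so the 2 to 5 days in the Study Summary most plausibly describes the hospital phase. Its floor equals the endpoint window. For example, if surgery ends at 14:00 and the patient leaves at 10:00 on day 2, 44 hours have passed. Discharge at 36 h would usually fall overnight after a daytime operation, and day-1 discharge conflicts with the 2-day floor. Section 1.1 cites a study whose title mentions a 23-h stay, but cites it because "it has had promising results for analgesia after colorectal surgery". It gives no discharge rate for this trial.

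**Reading 1: unseen hours count as zero.** Assumptions: SD equal to mean; a fraction f = 0.3 to 0.5 of use falls in hours 24-48, evenly spread; leaving is unrelated to need. Then

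shift in SD = (share of the 48-h total lost) × (arm difference in early discharge).

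| Discharge | Share lost | Arm difference 0.1 to 0.3: shift |
|---|---|---|
| 44 h | f × 4/24 = 0.05 to 0.083 | 0.005 to 0.025 SD |
| 36 h | f × 12/24 = 0.15 to 0.25 | 0.015 to 0.075 SD |

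With 100 per arm and no true difference, a shift of 0.025 SD gives 5.4% rejection by the t-test and 0.075 SD gives 8.2%. If the SD is only 0.75 of the mean, the largest 44 h shift is 0.025/0.75 = 0.033 SD and rejection is 5.6%. An 18% rejection rate (shift 0.15 SD) would need half of the total lost and a 30-point arm difference.

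Simulation with log-normal totals, where leavers need less opioid (latent correlation 0.3), gives smaller shifts. At 44 h, with 10% against 20% or 40% leaving early, they are 0.004 to 0.020 SD, with log-scale t-test rejection of 5.0-5.7%. At 36 h, with 10% against 20, 30 or 40%, they are 0.012-0.020, 0.023-0.037 and 0.038-0.062 SD.

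**Reading 2: the total is missing and the patient is left out.** If leaving is unrelated to need, the bias is zero. With correlation 0.3 it runs the other way, and the hour of discharge no longer matters:

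| Early discharge by arm | Share missing (mean of the two) | Bias | Above 10%? |
|---|---|---|---|
| 2% v 7% | 4.5% | 0.02 SD | no |
| 5% v 15% | 10% | 0.04 SD | no |
| 10% v 20% | 15% | 0.035 SD | yes |
| 10% v 30% | 20% | 0.075 SD | yes |
| 10% v 40% | 25% | 0.112 SD | yes |

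So where the bias exceeds about 0.04 SD in these cases, the imputed sensitivity analysis is already required. On precision, dropping 10% from 100 per arm leaves 76.1% power at 0.40 SD. The planned total is 226, or 113 per arm, and 113 × 0.90 = 101.7, so a loss of that size still leaves about 100.

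**Equal rates (20% v 20%).** No bias; rejection 4.7-5.3%.

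**The case for a change.** The best case for a change runs as follows. The plan adjusts pain for observation time, so it expected unequal follow-up, yet it gives the opioid total over the same window no matching rule. Two competent analysts could follow the text and err in opposite directions, and in an open trial that choice is better not left until the data are seen. On the assumed inputs, with 10% against 40% leaving early, null rejection reaches 10.9% for the truncated sum (log-scale t-test, discharge at 36 h) and 12.9% when early leavers are dropped. A few sentences and multiple imputation would remove most of this: in simulation the bias was then at most 0.008 SD, with rejection of 4.2-5.3%.

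The omission stands, and so does the arithmetic. The upper figures do not carry over to this trial. They need a 30-point arm difference in early discharge, which nothing in the documents supports. For the truncated sum they also need discharge well inside the 2-day floor and half of all use in the second day. For the dropped patients they need an assumed link between leaving and opioid need.

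The two readings are not equally natural either. The endpoint is 48-hour use determined for each patient, and a shorter sum is not that. Such a patient lacks the necessary data, and the missing-data text then applies. That text governs the analyses generally, so it qualifies the modified intent-to-treat set and does not contradict it.

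The imputation result is also flattering. It assumes that the share of use after hour 36 does not depend on leaving, which nobody can check for hours spent at home. If leavers use half as much in the unseen hours, the truncation bias at 10% v 40% halves to 0.018-0.030 SD. Recording home use or using a rate per hour observed would be equally defensible, so imputation as the primary analysis trades one assumption for another.

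**Conclusion.** No change follows. The plan leaves a detail unwritten; it does not state a rule that gives a wrong answer. The gap is one that analysts fill sensibly: an incomplete total is recognised as incomplete, the record is searched, and above 10% missing the imputed re-analysis runs. Below that level, the cases examined give a bias of about 0.02 to 0.04 SD even when leavers need less opioid.

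In the setting that best fits the documents, discharge a few hours short of 48, counting the unseen hours as zero moves the contrast by at most about 0.025 SD (0.033 SD if the SD is three quarters of the mean). That is under a tenth of the 0.4 SD target, with rejection near 5-6%. The effect vanishes if early discharge is equal by arm, and the two readings err in opposite directions, so the documents support no predicted direction. Sample size, power and the pain endpoint are unaffected.

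This rests on reading 2 to 5 days as the hospital phase and on assumed OME distributions and discharge rates. Many discharges well before 44 h, at clearly different rates by arm, would make the point weightier. Length of stay is a planned endpoint, so that pattern would be visible in the trial's own data.

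### Section 7.3 does not fix one test for the co-primary OME endpoint, and none of the tests it lists uses the randomisation strata

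*Combined protocol and SAP*

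**What the plan says.** Section 7.2 makes cumulative 48-hour OME a primary endpoint beside pain AUC. It sizes the trial at 100 per arm for "an effect size of 0.40 using a two group t-test" and puts the OME difference worth detecting at 0.4 SD of the mean.

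For OME, section 7.3 first says: "The difference in mean standardized OME will be compared with a two-sample test". The type of test is not named; read with 7.2 it is most naturally a t-test on the raw scale. For a skewed distribution, "a two-sample t-test will be performed on the logged values of OME or a Wilcoxon rank sum test will be used", the Wilcoxon test being on untransformed values. No section gives a skewness statistic, a threshold, a normality test or a blinded data review, and none ranks the two alternatives.

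Two comparisons in the same section help. Pain AUC has a single fixed t-test. Length of stay, a secondary endpoint, names only one alternative: "If there are outliers, a Wilcoxon rank sum test will be used". Its trigger is also undefined, so it is more fixed than OME only in having one fallback.

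Section 7.1 stratifies the randomisation by type of surgery (minimally invasive or open) and by site. None of the OME tests in 7.3 uses these factors. The only adjustment foreseen is a secondary regression on baseline variables found to be unbalanced.

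**The concern.** The candidate tests answer different questions: a difference in means (the scale of 7.2), a ratio of geometric means, or a shift in ranks. A report could follow 7.3 to the letter and present any of the three as the primary OME result. Different choices can also give different verdicts on significance.

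If the choice were made after seeing the p-values, the OME error rate would exceed 0.05. Section 7.3 has no slack to absorb this, because it already adds the two endpoints up to say that "the overall two-sided level of significance for the trial will be 0.10".

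Leaving out the strata is a separate weakness of the same sentences. When surgery type and site affect opioid use, an unstratified test ignores variation that the randomisation was designed to balance, which makes it conservative and less powerful.

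**Working it through.** **1. The plan's own figures.** Inputs from 7.2: n = 100 per arm, two-sided 0.05, effects of 0.40 and 0.50 SD. Noncentral t with 198 df and noncentrality d·√(n/2): 0.40 × √50 = 2.83 gives 80.4% power, and 0.50 × √50 = 3.54 gives 94.0%. The stated 80% and 94% reproduce, so there is no arithmetic error. The stated overall level is the sum 0.05 + 0.05 = 0.10.

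**2. Assumptions for the rest.** The documents give no OME distribution. Assumed: OME = 60·exp(N(0, s)), with log-SD s from 0.3 to 1, 100 per arm and no zeros; 20,000 simulated trials per scenario (Monte Carlo standard error at 5%: √(0.05 × 0.95 / 20,000) ≈ 0.15 points).

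**3. Disagreement between analysts who see only the pooled shape.** The effect is 0.4 log-SD. *Shared trigger*: both leave the raw t-test when pooled skewness exceeds 1; one then uses the log t-test, the other Wilcoxon. *Different triggers*: one moves to Wilcoxon above skewness 1, the other to the log t-test above skewness 2. The thresholds are illustrative.

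| Log-SD | Disagree on significance, shared trigger | Disagree, different triggers |
|---|---|---|
| 0.3 | 1.9% | 2.7% |
| 0.4 | 3.9% | 6.8% |
| 0.5 | 5.0% | 9.1% |
| 0.75 | 5.3% | 7.3% |
| 1.0 | 4.9% | 5.7% |

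Under the null, each of the two rules in the last column keeps type I error at 4.7–5.2%.

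**4. If the smaller p-value of the two tests for skewed data were reported.** At log-SD 1 under the null, the log t-test and Wilcoxon each reject in about 5% of trials and disagree in about 2%. At least one rejects in 5.9–6.1%. Adding the endpoints as 7.3 does: 0.05 + 0.06 = 0.11. If the two endpoints were independent: 1 − 0.95 × 0.94 = 0.107. With 10% zeros and log(OME + 1), the OME figure is 6.4–7.5% for log-SD 0.5 to 1.2, so 0.11 depends on the no-zeros assumption.

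**5. Stratification.** Assumed: 50% minimally invasive, a 70:30 site split, log effects of 0.5 for open surgery and 0.2 for site; 6,000 trials, 100 per arm, effect 0.4 log-SD.

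| Log-SD | Null rejection, van Elteren / unstratified Wilcoxon | Power, van Elteren / unstratified Wilcoxon |
|---|---|---|
| 0.5 | 5.1% / 2.8% | 77.5% / 69.8% |
| 1.0 | 4.8% / 4.0% | 78.2% / 76.7% |

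**6. Zeros.** The log test is undefined for a patient who uses no opioid. With 10% zeros assumed, log-SD 1 and an effect of 0.4 log units, its power is 22%, 35% or 55% when the added constant is 0.1, 1 or 10.

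**The case against.** Conditional wording of this kind is common, and a sensible analyst would judge skewness from pooled data. That stands: such a choice costs almost nothing in type I error, and with a shared trigger the disagreement is about 2–5%. The undefined trigger alone would be little more than a missing detail.

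Three stronger readings are tempting, and the documents do not support them.

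- A reader might infer that three tests are open in every data set and take the best of three as the error rate. But 7.3 offers the raw-scale test only when data are not skewed. At log-SD 1, pooled skewness exceeds 1 in every simulated trial and 2 in 96–97%, so the raw test would not be on offer there. What remains is the choice between the log t-test and Wilcoxon.
- A reader might infer that the test will be picked with results by arm in view, because the study is open (5.8) and 9.2 mentions quarterly interim analysis. The sentence in 9.2 concerns data processing and names no endpoint. The plan does not rule such a choice out, but it does not announce one.
- A reader might infer that patients with zero OME would be dropped under "Analyses will be done using all patients who have the necessary data for the analysis". That rule concerns missing data, and a recorded zero is not missing. Nor do the documents say that zeros will occur; the Wilcoxon branch would need no rule for them.

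It is also fair to object that moving from means to ranks changes the primary target and goes further than the gap requires. It is therefore offered below as a choice.

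**Conclusion.** The point holds in a limited form. Section 7.3 does not determine the test for a primary endpoint, and the tests it lists leave out the randomisation strata. In practice, two faithful readings can differ on significance in about 2–5% of trials with a shared trigger and up to about 9% without one. Type I error stays near 5% if the choice rests on pooled shape. It would be about 6% for OME, and up to about 0.11 overall, only if the choice between the two tests followed the p-values.

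These sizes assume log-normal OME, 100 per arm and no zeros. The gain from stratifying rests on assumed stratum effects: clear at log-SD 0.5, small at 1. The textual gap depends on none of this. The sample size calculation is sound, and no extra patients are needed. The plan should be corrected, but the gap does not undermine the trial.

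**What to change.** Before any comparison of OME by arm, replace the OME test sentences in 7.3 with one primary test at two-sided 0.05, stratified by surgery type and site. Apply it to the modified intent-to-treat set ("an analysis of all randomized patients who did not withdraw prior to surgery") with OME data, with no use entered as 0. Make the other tests sensitivity analyses; any log analysis should state its added constant. The sponsor should choose between two options.

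- **Ranks.** Van Elteren (stratified Wilcoxon) test on untransformed 48-hour OME, with the stratified mean difference and its 95% CI reported beside it. Section 7.2 must then say that the OME test no longer targets the mean difference.
- **Means.** A stratum-adjusted comparison of mean OME with a robust 95% CI. This keeps the target of 7.2 and closes the gap equally well.

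**Cost.** Either option is a change of wording with no extra patients, but the first also changes what the primary test measures. If OME is near normal, the rank test loses about 2–3 points of power at 0.4 SD: 80.4% to 77.5% at 100 per arm, and 85.3% to 83.4% at 113 per arm (226 / 2). It can also reject when means are equal. With log-SDs of 1.0 and 0.8 and medians of 60 and 71.8 (means 60·e^0.5 ≈ 71.8·e^0.32 ≈ 98.9), the unstratified Wilcoxon test rejects in 27.6% of simulated trials. That is why the mean difference must be reported beside it.

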1.4 Dose Rationale and Risk/Benefits

After induction of anesthesia, the patients will receive a single injection with 133 mg of EXPAREL suspended in 20mL of injectable saline, in each side, in the transversus abdominis plane (TAP). The injection will be ultrasound guided, and performed by our interventional anesthesiologists. The risks are the same as any non-EXPAREL TAP block, which include bleeding, infection, and pain. Systemic absorption of EXPAREL is possible, but as above (section 1.3), the side effects have not been found to be any different than the use of ordinary bupivacaine.

The risks will be included in the consent form, which include arrhythmias, bleeding infection, pain, and are no different than the use of TAP Bupivacaine, which is a standard of practice in our institution.

The alternate treatment group (the control group) will receive 100 mcg hydromorphone in a single intrathecal injection, administered by our interventional anesthesiologists immediately preoperatively. This is currently used routinely in the colorectal practice, as well as other practices across the enterprise.

2 Study Objectives

Primary Objective

To assess efficacy of EXPAREL TAP blocks in improving pain scores for 48 hours postoperatively, and in reducing total oral morphine equivalents (OME) use, compared to standard Intrathecal opioid administration (IT).

[figure not shown]
Secondary Objective

Assess the length of stay (LOS), postoperative ileus (POI) incidence, and the use of intravenous patient controlled analgesia (PCA) in patients that had EXPAREL TAP blocs compared to IT.

3 Study Design

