3.2 Primary Study Endpoints

Primary end points include mean pain scores for 48 hours and OME use associated with IT and EXPAREL TAP.

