5.8 Masking/Blinding of Study

The study will not be blinded.

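### Do the two primary endpoints in Section 7.3 need a stated cut-off and a rule for a split result?

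*Combined protocol and SAP*

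**What the plan says.** Section 3.2 names the pair: "Primary end points include mean pain scores for 48 hours and OME use associated with IT and EXPAREL TAP". The primary objective in Section 2 also joins them, looking for benefit "in improving pain scores for 48 hours postoperatively, and in reducing total oral morphine equivalents (OME) use".

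Section 7.2 sets the size. "A sample size of 100 patients per arm provides 80% power to detect an effect size of 0.40 using a two group t-test", at a two-sided 0.05, where the effect size is the difference in mean AUC over the within-group SD. For a 0.50 SD difference in pain it adds: "This study is adequately powered to detect this; a sample size of 100 patients in each group has 94% power". For opioid use it gives no separate power, only the view that "a difference of 0.4 standard deviations in the mean narcotic use (standardized to OME) between the groups is clinically meaningful".

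Section 7.3 compares each endpoint with its own two-sample test, allowing a log transform or a rank test for skewed OME. It then says "A two-sided p-value will be declared statistically significant for each primary endpoint" and, directly after, "This will mean that the overall two-sided level of significance for the trial will be 0.10". No sentence covers the case where one endpoint is significant and the other is not.

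**The concern.** Three things look wrong.

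1. The decision sentence has no number, so read literally it declares any p-value significant.
2. An error level for the trial as a whole normally goes with a definition of a positive trial, and there is none. The two natural definitions, *at least one endpoint* and *both endpoints*, disagree whenever exactly one is significant. The *and* in Sections 2 and 3.2 could be read as requiring both.
3. The 80% and 94% in Section 7.2 are powers for one test, not for either trial-level definition.

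At stake is the verdict after a split result. Section 5.8 states "The study will not be blinded", and Section 9.2 has the data combined quarterly with an interim analysis. An open rule could therefore be settled once it was known which endpoint had won.

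**Working it through.** **Inputs.** 100 per arm, effects of 0.40 and 0.50 SD, and two-sided 0.05 (Section 7.2); overall 0.10 (Section 7.3); 226 enrolled (Study Summary). The correlation between endpoints is not given, so 0 to 0.9 is assumed, with normal data and t-tests.

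**Step 1: the plan's own powers.** Noncentrality = d × √(n/2), with 198 degrees of freedom and critical value 1.972.
- d = 0.40: 0.40 × √50 = 2.83; power 80.4% (stated 80%).
- d = 0.50: 0.50 × √50 = 3.54; power 94.0% (stated 94%).

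Both reproduce.

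**Step 2: which rule gives 0.10?**
- Separate tests at 0.05: the chance of at least one false positive is at most 0.05 + 0.05 = 0.10. With no true effect and independent endpoints it is 1 − 0.95² = 0.0975; at correlation 0.9 it is about 0.07.
- Both required: at most 0.05, reached when one endpoint has no effect and the other a very large one. With no effect on either it is 0.05² = 0.0025 at correlation 0 and about 0.03 at 0.9.

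Only the first rule yields the plan's figure, and only with 0.05 per endpoint if the split is equal. So the missing cut-off and the intended reading both follow from numbers already printed.

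**Step 3: how often the results split.** For independent endpoints with 0.40 SD on both:
- both significant: 0.8036² = 0.646
- at least one: 1 − 0.1964² = 0.961
- exactly one: 0.961 − 0.646 = 0.315

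Simulation of two correlated t statistics gives the rest of each range (correlation 0 to 0.9):

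| True effect, pain / OME (SD) | Exactly one | At least one | Both |
|---|---|---|---|
| 0.40 / 0.40 | 32% to 10% | 96% to 85% | 65% to 75% |
| 0.50 / 0.40 | 23% to 14% | 99% to 94% | 76% to 80% |
| 0.40 / 0 | 77% to 80% | 81% to 83% | 4% to 2.5% |

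A split is therefore a realistic outcome. The last row mostly restates single-endpoint power: a lone true effect is found about 80% of the time, and the other endpoint is correctly negative.

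**Step 4: is there a power shortfall under the reading the plan implies?** For separate claims, the relevant power is that of each test: 80.4% at 0.40 SD, rising to 84.9% if all 226 (113 per arm) are analysed. For at least one endpoint, the stated 80% is a floor: every figure in that column is at or above 81%. Only a both-required rule falls below 80%, and the 0.10 argues against that rule.

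**Step 5: what the alternatives would cost.**
- Requiring both: 111 to 130 per arm for 80% power at 0.40 SD on both, so 222 to 260 evaluable against 200, or 22 to 60 more.
- Hochberg at an overall 0.05: power for a lone 0.40 SD endpoint falls from 80% to 72%.
- Splitting to 0.025 each: 71.5% per endpoint at 100 per arm; 121 per arm (242 evaluable) to regain 80%.

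**The case for a change.** The best case for acting is that the remedy is only a sentence. A level stated for the trial invites a trial-level verdict, the study is open-label, and data are looked at quarterly. A reader could call a lone significant endpoint a success or a failure after the fact. If the sponsor did mean that both must be significant, power at 0.40 SD on both is 65–75% rather than 80%, and about 63% if the correlation were −0.3.

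Part of this stands. No sentence covers a split result, and one would be tidier. The 0.10 bound also assumes that the quarterly analyses do not test efficacy. Section 9.2 does not say what they test, which is a separate question from the two-endpoint rule.

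The rest does not carry. The 0.10 is presented as the consequence of judging each endpoint separately, and that consequence does not follow under a both-required rule. The *and* in Sections 2 and 3.2 reads as a list of endpoints. An added success rule can also do harm. Suppose the trial were called positive when at least one endpoint favours EXPAREL TAP. The 0.10 would then be wrong, because wins in one direction are bounded by 2 × 0.025 = 0.05 (1 − 0.975² = 0.049 if independent). The trial would also count as positive if the other endpoint significantly favoured intrathecal analgesia. Separate reporting of the two results, as the plan implies, avoids both faults.

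**Conclusion.** No change is called for. The omitted cut-off is a clerical slip: two-sided 0.05 per endpoint is recoverable from Section 7.2 and from the overall 0.10. The split-result gap is one that analysts fill sensibly, by testing each endpoint at 0.05, claiming a difference only for the endpoint that is significant and in its observed direction, and reporting both. The overall 0.10 is an openly stated trade-off that keeps 80% power per endpoint at 100 per arm; holding 0.05 overall would cost about 8 points of power for a lone endpoint, or 42 more evaluable patients (242 − 200).

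No printed figure is wrong. The conclusion rests on the separate-claims reading, on t-tests with roughly normal data (for OME the plan allows a log or rank analysis), on the assumed correlations, and on no efficacy testing at the quarterly analyses. It would differ only if the sponsor intended both endpoints to be required, which the plan's own 0.10 contradicts.
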